6.3 MEASURES TO MINIMIZE BIAS: RANDOMIZATION AND BLINDING

In the DRI15928 study, participants will be centrally assigned to 1 of 8 arms (4 dose groups in each of the 2 cohorts at equal ratio to start with SAR442168 (in Cohort 1) or placebo (in Cohort 2) period before cross-over, using an IVRS/IWRS.

During the double-blind period of LTS16004 study, participants will continue treatment with the dose of SAR442168 assigned during the DRI15928 study. Investigators will remain blinded to each participant's assigned cohort (sequence) and dose during the double-blind period of the study.

Blind break (IVRS/IWRS)

The IVRS/IWRS will be programmed with blind-breaking instructions. In case of an emergency, the Investigator has the sole responsibility for determining if unblinding of a participant's treatment assignment is warranted. Participant safety must always be the first consideration in making such a determination. If the Investigator decides that unblinding is warranted, the Investigator should make every effort to contact the Sponsor prior to unblinding a participant's treatment assignment unless this could delay emergency treatment of the participant. If a participant's treatment assignment is unblinded, the Sponsor must be notified within 24 hours after breaking the blind. The date and reason that the blind was broken must be recorded in the source documentation and case report form, as applicable.

Methods of blinding

During the double-blind period of this study, this study is blinded for SAR442168 dose. Participants will continue treatment with their same SAR442168 dose used in the DRI15928 study.

During the double-blind period of this study, Investigators will not have access to MRI data except for any non-MS related findings, which will be communicated in order to evaluate the safety of the participant. The radiology service for the site will be in charge of timely reporting of any non-MS findings on MRI to the Investigator.

The IDMC will be used to periodically monitor safety data from this study. During the double-blind period of this study, unblinded data will be provided for IDMC review by an unblinded independent statistician. Study team members, Investigators, and study participants will not have access to unblinded data.

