1.3 DETERMINATION OF SAMPLE SIZE

There are no sample size calculations for this long-term extension study.

All participants who completed the DRI15928 study were eligible for enrollment in the LTS16004 study. The Sponsor enrolled 130 participants in the DRI15928 study, 129 completed the study treatment, and 126 enrolled in LTS16004.

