2 STATISTICAL AND ANALYTICAL PROCEDURES

2.1 ANALYSIS ENDPOINTS

2.1.1 Demographic and baseline characteristics

The baseline value is defined as the baseline value from the DRI15928 study. Data for demographic and baseline characteristics will be from study DRI15928 database for participants who enrolled in LTS16004.

All baseline safety and efficacy parameters (apart from those listed below) are presented along with the on-treatment summary statistics in the safety and efficacy sections.

Demographic characteristics

Demographic variables are gender (Male, Female), race (Caucasian/white, Black, Asian/Oriental, American Indian or Alaska Native, Native Hawaiian or other Pacific Island, other), age in years (quantitative and qualitative variable: ≤ 40 , > 40 years), and ethnicity (Hispanic, non-Hispanic).

Medical or surgical history

Medical and surgical history data in DRI15928 will be recoded to PT and associated primary SOC using the version of MedDRA in use at Sanofi at the time of LTS16004 database lock. Any new past and/ or concomitant diseases or past surgeries since the end of DRI15928 will also be included.

Substance use - alcohol habit

The frequency of alcohol use in the last 12 months prior to entry into DRI15928.

Multiple sclerosis history and disease characteristics at baseline

MS history and disease characteristics as defined in DRI15928 including time since first symptoms of MS (years), time since diagnosis of MS (years), time since most recent relapse onset (months), MS type (relapsing remitting, secondary progressive), number of relapse(s) within the past year and within the past 2 years (quantitative and qualitative: 0, 1, 2, ≥ 3), baseline EDSS score (quantitative and qualitative). All are relative to DRI15928 randomization visit.

MRI parameters at baseline

MRI parameters at DRI15928 baseline include count of Gd-enhancing T1 hyperintense, T2, and T1 non-enhancing (hypointense) lesions, volume of T2 and T1 non-enhancing (hypointense) lesions, and normalized brain, cerebral cortex, and thalamic volume.

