ARR will be analyzed using a negative binomial regression model in the mITT population. The model will include the total number of confirmed relapses with onset between first and last IMP doses in LTS16004 as response variable and dose group (5/60, 15/60, 30/60, and 60/60 mg) as covariate. Log transformed standardized treatment duration will be included in the model as an "offset" variable. The estimated ARR for each dose group and corresponding 95% 2-sided CI will be derived from the negative binomial model. The relative reductions in ARR (60/60 mg versus each other dose group) along with 95% CIs will be estimated from the model.

Number of participants with 0, 1, 2, 3, 4, or ≥ 5 relapses will be presented by dose group, namely, 5/60, 15/60, 30/60, and 60/60 mg.

The ARR for the tolebrutinib 60 mg treatment period will be analyzed using a negative binomial regression model, as well. Only relapses with onset during the tolebrutinib 60 mg treatment period will be counted, which means Part B only for participants originally assigned to 5, 15 and 30 mg dose groups and Parts A and B for participants originally assigned to the 60 mg dose group. Excluded are patient years and relapses during the first 8 weeks of tolebrutinib treatment after the switch to Part B for participants in the 5/15/30 to 60 mg groups and the same for participants in the 60/60 mg dose group, if the sum of the placebo run-out period (if applicable) and any gap period is >4 weeks. The negative binomial regression model will use total number of relapses as the response variable and log transformed standardized treatment duration as an "offset" variable. The estimated ARR and the 95% CI will be provided.

The number of participants with 0, 1, 2, 3, 4, or ≥ 5 relapses during the tolebrutinib 60 mg treatment period will also be presented.

Proportion of participants relapse free

Time to first confirmed relapse in LTS16004 is defined as "the date of first relapse - first IMP date (in LTS16004) + 1". If the participant has no relapse before treatment discontinuation/completion, then the participant will be considered as free of relapse until the date of treatment discontinuation/completion. His/her data will be censored after this date. The proportion of participants without confirmed relapse in LTS16004 will be estimated based on the Kaplan-Meier curve at yearly time points (1, 2, 3, 4 and 5 years since first IMP in LTS16004).

Change from baseline in EDSS scores

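### The ARR model adjusts for dose group only, although prior-year relapse count is already held; adding it is a small, nearly free improvement

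*SAP*

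**What the plan says.** SAP 2.4.4, under the annualized relapse rate, fits a negative binomial model to confirmed relapses in LTS16004 with "dose group (5/60, 15/60, 30/60, and 60/60 mg) as covariate". "Log transformed standardized treatment duration will be included in the model as an" offset. For each group's rate the "corresponding 95% 2-sided CI will be derived from the negative binomial model". The SAP then adds between-group estimates: "The relative reductions in ARR (60/60 mg versus each other dose group) along with 95% CIs will be estimated from the model". The same section also gives a gross rate, relapses divided by follow-up time, by dose group.

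SAP 2.1.1 lists among the baseline data taken from DRI15928 the "number of relapse(s) within the past year and within the past 2 years", counted back from the DRI15928 randomization visit. SAP 2.4.1 tabulates these by dose group. They do not enter the relapse model, no adjusted sensitivity analysis is planned, and no reason for the omission is given.

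On numbers, SAP 1.3 states: "The Sponsor enrolled 130 participants in the DRI15928 study, 129 completed the study treatment, and 126 enrolled in LTS16004". Protocol 6.3 says that in the parent study participants were "centrally assigned to 1 of 8 arms (4 dose groups in each of the 2 cohorts at equal ratio".

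**The concern.** The SAP chose to estimate ratios between groups and put intervals on them, so readers will interpret them. In groups of about 31, relapse history can differ by chance, and a dose-only model cannot separate that difference from a dose effect. The true contrast may also be modest, because every group moves to 60 mg in Part B. A few percent of chance shift is then not negligible beside it.

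Timing matters as well. Baseline relapse history will be tabulated by dose group. If a difference shows up, any adjustment added then is post hoc, whereas naming the covariate before lock avoids that. The sponsor has used this approach before: Protocol 2.3 and 4.3 report the parent-study lesion result from a negative binomial model adjusted for baseline Gd-enhancing lesion activity.

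**Working it through.** The documents give no sample size calculation, relapse rate or dispersion, so there is no plan figure to reproduce. The check asks how much the omission could cost.

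**Inputs from the documents**
- 126 enrolled (SAP 1.3) in 4 dose groups: 126/4 = 31.5 per group if retention was even. Counts by dose are not given.
- Month 60 with 28-day months (Protocol 1.3): 60 × 28 = 1680 days; 1680/365.25 = 4.60 years.

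**Assumed inputs**
- ARR 0.1 to 0.3; dispersion k 0.5 to 2.
- Prior-year relapses 0/1/2/3 with probabilities 0.10/0.60/0.22/0.08 (mean 1.28, SD about 0.75).
- Rate ratio b per prior relapse: 1.1, 1.3 or 1.5.

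**Precision**

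SE(log ratio) = √[2(1/μ + k)/n], with μ = ARR × 4.60 and n = 31.5. Adjustment removes the part of k explained by history: k_adj = (1 + k)/(1 + CV²) − 1, where CV² is the squared coefficient of variation of b^X and X is the prior-year count.

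- Example: ARR 0.2, k = 1, b = 1.3. μ = 0.92 and 1/μ = 1.087. CV² = 0.044, so k_adj = 2/1.044 − 1 = 0.915. The SE goes from √[2 × 2.087/31.5] = 0.364 to √[2 × 2.002/31.5] = 0.357, a fall of 2%.
- Largest gain in the range: ARR 0.3, k = 0.5, b = 1.5. μ = 1.38, 1/μ = 0.725, CV² = 0.115, k_adj = 0.345. The SE goes from 0.279 to 0.261, a fall of 6.6%.

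| Rate ratio per prior relapse | Fall in SE over the assumed range |
|---|---|
| 1.1 | under 1% |
| 1.3 | about 1–3% |
| 1.5 | about 3–7% |

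The unadjusted 95% CI factor, exp(1.96 × SE), runs from about 1.7 to 2.7 over the same range. A simulation of 126 participants with 15% early stopping gave falls of 0–4% in the model SE and 0–5% in the empirical SD. For the example setting the CI factor went from 2.10 to 2.09, and in the best case from 1.81 to 1.76. Some fits raised convergence warnings, so I rely more on the closed form.

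**Chance imbalance**

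With an assumed SD of 0.8 prior relapses, the SE of a difference in means between two groups is 0.8 × √(2/31.5) = 0.20. A difference d multiplies the rate ratio by b^d.

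| b | 1-SE imbalance (0.20) | 1.96-SE imbalance (0.395) |
|---|---|---|
| 1.1 | 1.019 | 1.038 |
| 1.3 | 1.054 | 1.109 |
| 1.5 | 1.085 | 1.174 |

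**How to report adjusted rates**

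Under a log link, the rate predicted at the mean covariate value is b^mean, while the population rate is proportional to E[b^X]. With the assumed distribution and b = 1.3, 1.3^1.28/1.428 = 0.980, so the rate at the mean is 2% too low. With b = 1.5, 1.5^1.28/1.765 = 0.952, about 5% too low. If history were Poisson with mean 1.2 and b = 1.65, it would be 1.65^1.2/exp(1.2 × 0.65) = 0.836, about 16% too low. Such an error could cancel or exceed the gain in precision, so the rates should be standardised over the observed histories.

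**Cohort**

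Adding DRI15928 cohort with an assumed rate ratio of 1.2 left the simulated SE ratio, adjusted to unadjusted, essentially unchanged: 0.990, against 0.991 with no cohort effect.

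**The case against.** The best defence is that nothing planned depends on this. The protocol states no hypothesis and its synopsis plans no comparison between treatment groups; the SAP calculates no p-values, and safety is primary. Dose was randomized in the parent study and nearly everyone rolled over, so the dose-only ratio is unbiased on average. All groups share the 60 mg dose in Part B. Imbalance will be visible in the baseline tables, and a gross ARR is already planned. All of this stands, and it limits the point to a minor one. It does not remove it, because the SAP still commits to the ratios and their intervals.

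Two stronger readings are tempting. A reader might infer that the planned ratios are biased or their intervals invalid; randomization rules out the first, and nothing in the documents supports the second. A reader might also infer from the 8-arm allocation that cohort is a stratum wrongly left out. Cohort is only the order of a short placebo period, and doses were allocated at equal ratio within each cohort, so it should be near-balanced across doses. The documents do not describe it as prognostic for relapses. Where the placebo run-out could matter, the 60 mg ARR analysis in SAP 2.4.4 already has an exclusion rule that counts it.

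**Conclusion.** The point holds as a low-severity improvement. The dose-only model is legitimate, but it leaves unused a baseline count that is already held. Under the assumed rate ratios of 1.1 to 1.5 per prior relapse, the omission costs about 0–7% of the standard error. It also exposes a ratio to a shift of about 2–8.5% at a 1-SE imbalance, or 4–17% at 1.96 SE. Protection against imbalance is the better argument; the precision gain alone would hardly justify a change. The intervals stay wide with or without the covariate, because of the sample size and the number of events, so the model should not be blamed for their width.

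That prior relapses predict later ones in this population is itself an assumption. If they do not, adjustment gains nothing and costs one parameter.

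**What to change.** Before database lock, amend the between-group ARR model in SAP 2.4.4 as follows.

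- Add the number of relapses in the year before DRI15928 randomization as a covariate, keeping dose group and the offset.
- Report group ARRs by marginal standardisation: average the predicted rate over the observed relapse histories of the whole mITT population with each dose group set in turn. Do not evaluate at the covariate mean. Show the gross ARR already planned beside these.
- If a participant's history is missing, use the overall mean. A dose-group mean would make a baseline value depend on the assigned group.
- Do not add cohort.

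The cost is a few lines in the SAP and no new data. The downside is one more parameter in a model with few events.

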- Dose regimen: once daily.

Noninvestigational medicinal products

A radiological, signal-enhancing, intravenous (IV) contrast medium will be used for T1-contrast-enhanced MRI sequences. A locally approved contrast agent will be used.

Due to a potential safety risk related to gadolinium (Gd) deposition in the brain seen with certain contrast agents, these agents should be used in accordance with local recommendations and regulations. Otherwise, use of these agents will be similar to their routine use and will be sourced locally. The study manual will provide more details describing their administration in this trial.

Continued access to intervention after the end of the study

After the end of this study, participants who successfully complete the trial on SAR442168 may be offered the option to participate in a Phase 3 long-term safety (LTS) study for up to an additional 3 years, or until SAR442168 is approved in their respective country, whichever comes first. Details of the Phase 3 LTS study will be described in a separate protocol. If this program is terminated earlier, other available RMS treatments will need to be considered at the discretion of the treating physician.

Statistical considerations:

No statistical comparisons between treatment groups will be made. Summaries using descriptive statistics will be provided by visit for parameters.

Sample size calculations:

There are no sample size calculations for this long-term extension study. Sample size will be based on the elective participation of participants who complete the DRI15928 study, meet the eligibility criteria, and enroll in this LTS16004 study.

Primary analysis:

The safety of long-term SAR442168 treatment will be evaluated using descriptive statistics, summarizing incidence of adverse events (Aes), serious adverse events (SAEs), and clinically significant abnormalities (PCSAs) for clinical laboratory tests, and summarizing safety findings on MRI, electrocardiogram (ECG), and vital signs parameters by visit.

Analysis of secondary endpoints:

[figure not shown]
Summaries using descriptive statistics will be provided by visit.

Independent Hepatology Assessment Committee: Yes

Data Monitoring Committee: Yes

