4.2 SCIENTIFIC RATIONALE FOR STUDY DESIGN

Until the start of Part B of this study, participants will continue treatment with their same SAR442168 dose used in the DRI15928 study. The double-blind period (ie, Part A) will reduce the potential for bias in the evaluations and data collection to support safety and efficacy of several doses of SAR442168 beyond 12 weeks of treatment, and pooled analysis to evaluate efficacy and safety.

Open-label treatment with the selected Phase 3 SAR442168 dose during Part B will provide long-term safety data on SAR442168. Efficacy data will be collected as supportive data. Open-label treatment should introduce minimal bias for interpreting MRI and other endpoints such as biomarkers and protocol defined MS relapse. Moreover, regular training of EDSS assessors will help minimize potential bias for interpreting disability outcomes.

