8.1.2.2 Definition of multiple sclerosis relapse

For the purposes of this study, MS relapse is defined as acute, new neurological symptoms or worsening of previous neurological symptoms with an objective change on neurological examination. Symptoms must:

- Be attributable to MS.
- Last for ≥ 24 hours, with or without recovery.
- Be present at normal body temperature (ie, no infection, excessive exercise, or excessively high ambient temperature), and
- Be preceded by ≥ 30 days of clinical stability (including no previous MS relapse).

Note: An exacerbation or recurrence of symptoms and signs that can be reasonably attributed to transient impairment of conduction in previously demyelinated pathways due to drugs (such as rarely occurs a few hours after injection of interferon beta), raised core body temperature (the Uhthoff phenomenon), or systemic cytokine release will not be considered a relapse.

It is at the Investigator's discretion and responsibility to choose the best treatment option for any MS relapse, such as a high dose glucocorticoid treatment course.

Analysis of relapses will be detailed in the Statistical Analysis Plan.

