9 STATISTICAL CONSIDERATIONS

9.1 STATISTICAL HYPOTHESES

This is a long-term safety and efficacy follow-up study for participants who have been treated with SAR442168, therefore, there is no statistical hypothesis assumed.

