9.4 STATISTICAL ANALYSES

The statistical analysis plan will be developed and finalized before database lock, or an ad hoc interim analysis, and will describe the participant populations to be included in the analyses, and procedures for accounting for missing, unused, and spurious data. This section is a summary of the planned statistical analyses of the primary and secondary endpoints.

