9.4.1 Efficacy analyses

All efficacy analyses will be performed on the Efficacy Population.

Table 9 - Efficacy analyses

Endpoint	Statistical Analysis Methods
Secondary endpoints:	Overall summary using descriptive statistics, by visit.
Exploratory	The exploratory efficacy endpoints listed in Section 3 will be descriptively summarized.

Abbreviations: ARR: annualized relapse rate; EDSS: Expanded Disability Status Scale; Gd: gadolinium.

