2.4 STATISTICAL METHODS

Continuous data will be summarized using the number of available data, mean, SD, median, minimum, Q1, Q3, and maximum for each dose group. Categorical and ordinal data will be summarized using the number and percentage of participants in each dose group.

P-values will not be calculated.

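### Do the SAP's ARR ratios between dose sequences, with 95% CIs, break the protocol's statement that treatment groups will not be compared?

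*SAP*

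**What the plan says.** SAP section 2.4.4 counts confirmed relapses with onset between the first and last dose in LTS16004. It models them by negative binomial regression, with dose group (5/60, 15/60, 30/60, 60/60 mg) as the only covariate and log treatment duration as offset. The ARR of each group is given with a 95% CI, and then: "The relative reductions in ARR (60/60 mg versus each other dose group) along with 95% CIs will be estimated from the model." That makes three ratios. A second model estimates the ARR on 60 mg across all participants, with no group contrast. SAP section 2.4 adds: "P-values will not be calculated."

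The protocol synopsis, under statistical considerations, states: "No statistical comparisons between treatment groups will be made." Section 9.1 describes a long-term follow-up study, "therefore, there is no statistical hypothesis assumed." Table 9 in section 9.4.1 gives the method for secondary endpoints as "Overall summary using descriptive statistics, by visit."

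Other protocol text points toward a fuller relapse analysis. Section 8.1.2.2: "Analysis of relapses will be detailed in the Statistical Analysis Plan." Section 9.4: "This section is a summary of the planned statistical analyses of the primary and secondary endpoints." Section 4.2 says that the blinded Part A data are meant to "support safety and efficacy of several doses of SAR442168 beyond 12 weeks of treatment."

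**The concern.** The synopsis sentence has no qualifier, and it speaks of comparisons, not of tests. Three model-based ratios with 95% CIs are comparisons in ordinary usage, and each interval shows whether 1 is excluded. As written, the study report would contain estimates that the protocol says will not be made, and nothing in the SAP explains why.

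A second worry concerns meaning. The model covers Parts A and B together, and every participant who continues into Part B takes 60 mg. The ratio of 60/60 to 5/60 therefore compares 60 mg throughout with a later switch to 60 mg. Because the SAP calls these dose groups, a reader could take the ratio for 60 mg against 5 mg and conclude that dose matters little.

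**Working it through.** The plan states no power, alpha or sample size for this analysis, so there is no figure of its own to reproduce. The check is mainly a reading of the texts, with two short calculations.

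**1. What the synopsis sentence excludes.** Two readings are possible: no tests, or no between-group estimate of any kind.

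- Protocol 9.1 has no hypothesis. That rules out a test. It does not rule out an estimate with an interval, which needs no hypothesis.
- SAP 2.4 drops p-values, SAP 2.4.5 rules out routine testing of safety variables, and SAP 2.4.4 asks for efficacy summaries with measures of variability. All three fit the no-tests reading.
- Protocol 8.1.2.2 passes the relapse analysis to the SAP, and section 9.4 describes itself as a summary.
- The statistical section of the protocol (section 9) does not repeat the synopsis sentence.
- Table 9 is weak evidence either way. Its method is by visit, which does not suit a rate annualized over the whole treatment period.

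The no-tests reading makes the two documents consistent. The stricter reading rests on the synopsis sentence alone.

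**2. Whether the SAP already marks the ratio as a sequence contrast.**

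- The SAP uses two sets of labels: 5, 15, 30 and 60 mg for Part A alone (sections 2.4.3.1 and 2.4.5.1), and 5/60 to 60/60 for both parts together (sections 2.2, 2.4.4 and 2.4.5).
- The planned contrast uses the second set.
- SAP section 1.6 justifies the separate 60 mg analysis on the ground that, with everyone on 60 mg in Part B, pooling participants gives a better ARR for that dose. The authors therefore separated the rate by sequence from the rate at a dose.

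**3. What deleting the ratio would remove.** With group as the only covariate, the model gives ARR_g = exp(b_g) for each group. The ratio is

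exp(b_60/60) / exp(b_x/60) = exp(b_60/60 − b_x/60),

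which is the quotient of two displayed rates. Anyone can still form it after deletion. Only its interval would be lost.

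For scale, assume ARR 0.2, dispersion k = 1, an equal split of the 126 enrolled (n = 126/4 = 31.5) and full follow-up to Month 60 (1680 days).

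- Expected relapses per participant: m = 0.2 × 1680/365.25 = 0.92.
- CI factor for a ratio: exp(1.96 × √(2 × (1/m + k)/n)) = exp(1.96 × √(2 × 2.087/31.5)) = exp(1.96 × 0.364) = 2.04.
- A ratio of 0.87 would run from 0.87/2.04 = 0.43 to 0.87 × 2.04 = 1.78.
- With k = 0 the factor is 1.67; with k = 2 it is 2.38.

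An interval of that width warns the reader not to lean on the point estimate. A bare quotient of two rates gives no such warning.

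**4. How far a misreading could mislead.** The documents give neither the length of Part A nor any rate ratio, so this is illustration only. Let f be the Part A share of 240 weeks and RR the true Part A rate ratio, with equal rates in Part B:

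ratio over both parts = 1 / (f/RR + 1 − f).

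| Part A (weeks) | f | RR = 0.5 | Apparent reduction |
|---|---|---|---|
| 12 | 0.05 | 1/(0.10 + 0.95) = 0.952 | 4.8% |
| 36 | 0.15 | 1/(0.30 + 0.85) = 0.870 | 13.0% |
| 52 | 0.217 | 1/(0.433 + 0.783) = 0.822 | 17.8% |

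Protocol section 6.3 considers it unlikely that DRI15928 and Part A together last more than a year. The 52-week row is therefore an outer limit.

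These figures show what happens if the ratio is read as a dose effect. For the contrast of sequences, the same numbers are the correct answer.

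**The case for a change.** The strongest case for a change is that the synopsis says comparisons without qualification. Leaving out p-values does not turn a ratio with a 95% CI into a within-group description. Passing detail to the SAP does not license it to do what the protocol excludes. Section 4.2 can be satisfied by showing ARR by group, and the planned ratio does not isolate Part A in any case. Elsewhere the SAP separates Part A explicitly when it looks for dose trends in adverse events, but the ratio sentence has no such note. The repair would be a single sentence, deleted or added, at almost no cost.

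Part of this stands. The wording of the two documents does conflict if read literally, no passage reconciles it, and the SAP does call the sequences dose groups. Section 4.2 gives only indirect support for the ratio.

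It does not follow that the plan needs changing. The model is valid for the groups it names, the estimate is not biased for that contrast, and the only gain from deletion is closer agreement with one synopsis sentence. Against that, deletion loses the interval on a quotient that readers will form anyway. Statisticians could reasonably differ on that trade. A sentence stating that the ratio is descriptive and contrasts sequences would do no harm, but it would only repeat what the labels and the no-p-value rule already convey.

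**Conclusion.** No change follows. There is a real but minor mismatch in wording between the protocol synopsis and SAP section 2.4.4. Reading the synopsis as excluding hypothesis tests resolves it, and that reading fits the rest of both documents. The ratio is identifiable as a sequence contrast from its labels and from the separate 60 mg analysis. An analyst following the SAP would produce the same rates, intervals and ratios with or without a clarifying sentence.

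The effect on planned results is zero. Little depends on the ratio: ARR is a secondary endpoint, SAP section 3 describes the extension as supportive, and the 60 mg dose has already been selected. The conclusion rests on the no-tests reading of the synopsis and on the report keeping the x/60 labels. It does not depend on the assumed ARR, dispersion, group split or Part A length, which serve only to size a misreading.
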